8.2. Sample size determination

The sample size for the pilot study was determined as 10% of the total sample for the full RCT, which covers its feasibility nature. For the full RCT, assuming a 60% refusal rate, a significance level of 0.05, and a 5% difference between groups, a sample size of 900 participants per group would result in a power of 80%. Therefore, the estimated sample size for the pilot was 180 participants (90 per group).

8.3. Baseline Descriptive Statistics and Exploratory Analyses

Our exploratory analyses will use a comprehensive visual inspection of all variables. This process will include evaluating the frequency, percentage, and near-zero variance of categorical variables (e.g., gender and seven-day point prevalence abstinence), as well as analysing the distribution of numeric variables (e.g., age and scale scores) and their corresponding missing value patterns. Nearzero variance refers to situations where a categorical variable has few unique values compared to the sample size, making it almost constant. We will address near-zero variance by recategorising low-frequency categories. We will use univariate and bivariate plots, including histograms, bar plots, scatterplots, and pirate plots. We will also prepare tables with the frequency and percentage for categorical variables, as well as the mean and standard deviation for numeric variables. We will compare variables using a standardised mean difference (SMD), which is the difference in proportions or means divided by the pooled standard deviation. SMD magnitudes were interpreted according to the following criteria: SMD = 0.2 indicates a small effect, SMD = 0.5 indicates a medium effect, and SMD = 0.8 indicates a large effect. We will also present p-values for t-tests (for normally distributed numeric variables), Wilcoxon tests (for non-normally distributed numeric variables), and Chi-square tests (for categorical variables), considering p-values below 0.05 as statistically significant.

8.4. Statistical Analyses for Feasibility Metrics

We will use a line plot to assess the weekly cumulative recruitment rate for each participating institution, visualising trends over time and identifying recruitment bottlenecks. Additionally, we will analyse the proportion of eligible participants who consent, the dropout rate, and reasons for attrition to evaluate recruitment efficiency. To better understand recruitment efficiency, we will also measure the time from site initiation to the first participant recruitment at each centre.

To evaluate data collection quality, we will calculate the percentage of missing data for each variable and visualise missingness patterns to identify systematic issues. If the amount of missing data compromises further analyses, we will use imputation algorithms followed by sensitivity analyses to verify whether our results are stable with and without imputation.³³ Specifically, we will use the Multivariate Imputations by Chained Equations (MICE) algorithm,³⁴ which employs the fully conditional specification method,³⁵ where a separate model imputes each variable that contains missing data. We will use 100 multiple imputations and the predictive mean matching method for numeric variables, logistic regression imputation for binary variables, and polytomous regression imputation for categorical variables.

Furthermore, we will assess the mean time required to complete the Case Report Form (CRF) for both participants and staff, helping determine whether the data collection process imposes an undue burden.

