5.3. Strategies to avoid missing data and increase adherence

To reduce missing data, the pilot study has been designed to minimise the number of questions, avoiding participants feeling overwhelmed, which could lead to incomplete responses.

Within the app, certain responses will be required for participants to progress to the next steps or level up. While this approach is intended to increase engagement, some missing data may still occur. Additionally, phone call or email follow-ups have been considered for non-responders; however, challenges may persist, as this study targets a preventive population rather than patients, and might be less motivated to engage.

The pilot study will serve as a test for retention and adherence. Based on its findings, adjustments and mitigation strategies will be designed and implemented for the subsequent randomised controlled trial (RCT) to optimise participation and data completeness.

6. Study intervention(s) or experimental manipulation(s)

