8.1. Statistical hypotheses

The pilot study aims to assess the feasibility of a future larger RCT. It will also inform RCT planning, define the study protocol, and optimise the IBeChange intervention and study design.

Therefore, the statistical focus is on feasibility-related outcomes rather than formal hypothesis testing for clinical efficacy. The feasibility of the future RCT will be evaluated based on key metrics, including recruitment rates, completion rates, data completeness, and participant/staff feedback. The following feasibility hypotheses will guide our assessment

1. Recruitment Feasibility Hypotheses

- a. H₀ (Null Hypothesis): The recruitment rate will be insufficient for a future RCT, with an estimated rate below the predefined feasibility threshold (50% of eligible patients consent to participate).
- b. H₁ (Alternative Hypothesis): The recruitment rate will meet or exceed the feasibility threshold, indicating that the trial can recruit participants at an acceptable rate for an RCT.

2. Data Collection Feasibility Hypotheses

- a. Ho: The case report form (CRF) completion rate will be suboptimal, with excessive missing data (>10% missingness in primary outcomes).
- b. H₁: The CRF completion rate will be adequate, with minimal missing data, indicating good feasibility of data collection.
- 3. Acceptability and Usability Hypotheses
 - a. H₀: Participants will report low usability and satisfaction scores, assessed through the one single 0-10 visual analogue scale item per construct (mean score < 7)
 - b. H₁: Participants will report acceptable usability and satisfaction.
- 4. Operational Feasibility Hypotheses
 - a. Ho: The time required to complete each trial step (e.g., participant recruitment, data entry, and data transfer) will exceed the predefined thresholds (recruit 100% of participants within the first 3 months and complete data entry and transfer within 1 month of the end of the pilot).
 - b. H₁: The time required to complete each trial step will be within planned limits, supporting the feasibility of the future RCT.
- 5. Wearable usage Hypotheses
 - a. H₀: Participants in the wearable sub-group will not consistently use the wearable device, with fewer than 80% of participants using the device at least 4 days per week.
 - b. H₁: Participants in the wearable sub-group will consistently use the wearable device throughout the study.

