8.5. Analysis of Primary and Secondary Endpoints

The pilot data will be analysed to determine the potential effectiveness of the iBeChange platform and to enhance the recommendation system. The analysis will account for confounding factors and

within-subject correlation over time, providing valuable information for the larger RCT and improving the accuracy of the feedback provided by the recommendation system.

Both the pilot and future RCT will involve a Bayesian Adaptively Randomised Design (BARD).

Compared to traditional frequentist trials, BARDs tend to be more efficient. They require smaller sample sizes as they allow multiple interim analyses without statistical penalties, enabling protocol refinements according to predefined rules. These designs can adapt allocation rules, sampling procedures, and the number of treatments tested, and they include a data-driven stopping rule to halt a treatment if it is effective, futile, or harmful.^{36,37}

A Bayesian hierarchical modelling approach will be used to estimate intervention effects while accounting for site-level variability. We will use Bayesian multilevel models to evaluate the preliminary effectiveness of the IBeChange intervention on tobacco and alcohol consumption, nutrition, physical activity, and psychosocial outcomes while accounting for the grouping related to the longitudinal follow-up and the hierarchical structure of the data (i.e., multiple observations from the same participant over time as well as participants grouped in different institutions). When compared to single-level regression models, its Bayesian counterpart can assess the expected correlation between measurements of the same individual and individuals in the same group, accounting for the dependency of these observations. This is accomplished by dividing the total variance into variations associated with the groups (level-2) and individual participants (level-1). As a result, such models estimate the variance component for the second level (i.e., the variability of the participant-specific estimates) or higher levels, indicating that the findings are accurate and generalisable.^{38,39}

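### Section 8.4's only stability check on missing 12-week outcomes compares two analyses that both assume missing-at-random, so their agreement does not test that assumption

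*Protocol*

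**What the plan says.** Section 8.4 makes imputation conditional on missing data being serious enough to compromise the analyses. It then fixes the method: "Specifically, we will use the Multivariate Imputations by Chained Equations (MICE) algorithm", and "We will use 100 multiple imputations and the predictive mean matching method for numeric variables", with logistic and polytomous models for the other variable types. The check on the result is "we will use imputation algorithms followed by sensitivity analyses to verify whether our results are stable with and without imputation".

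The rest of the missing-data work in 8.4 is descriptive: "we will calculate the percentage of missing data for each variable and visualise missingness patterns to identify systematic issues", together with "the dropout rate, and reasons for attrition to evaluate recruitment efficiency". The only other sensitivity analysis, in section 8.5, concerns the priors.

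The analysis without imputation is the one in section 8.5: "We will use Bayesian multilevel models to evaluate the preliminary effectiveness of the IBeChange intervention". Section 4.4 measures effectiveness at baseline and 12 weeks only. On why people may not answer, section 5.3 says that "this study targets a preventive population rather than patients, and might be less motivated to engage".

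**The concern.** Standard MICE fills a missing 12-week value from participants who resemble the non-responder on observed data. A likelihood-based multilevel model fitted to the observed data relies on essentially the same condition. A strict complete-case analysis needs a related condition and gives no protection against outcome-related dropout either. Trial outcomes have only two time points, so a person lost before week 12 has no post-baseline trial outcome, and the two analyses draw on nearly the same information. They can agree closely and both be wrong.

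Low motivation is a plausible cause both of not answering and of not changing behaviour. Only the experimental arm has weekly missions, four-weekly habit assessments, two-weekly distress ratings (sections 6.2 and 6.2.1) and extra satisfaction and usability items at the end (section 7.2.1). Dropout that is related to outcome and differs by arm is therefore credible.

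The effect estimates matter beyond description. Section 8.6 allows early stopping on the posterior for the treatment effect, and section 8.8 feeds pilot effect sizes into the sample size of the full RCT.

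**Working it through.** **Plan's own figure.** Section 8.2 sets the pilot at 10% of the RCT: 0.10 × 2 × 900 = 180, or 90 per group. This reproduces and is not in dispute. It fixes the size of the simulated trial.

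**What the protocol does not give.** It gives no expected 12-week dropout rate and no dropout mechanism. The rates and mechanisms below are assumptions.

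**Simulation.** 90 per arm; outcome in SD units (higher is better); baseline–outcome correlation 0.5; true effect 0; 300 replicates. The analysis without imputation is a baseline-adjusted regression on responders, a frequentist stand-in for the Bayesian model. The analysis with imputation uses predictive mean matching, 100 imputations, with arm and baseline as predictors. In outcome-related dropout, the log-odds of dropping out rise by 1.5 for each SD by which the part of the 12-week outcome not explained by baseline is lower.

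| Assumed dropout, experimental / control | Without imputation | With MICE | Mean absolute gap |
|---|---|---|---|
| 10% outcome-related / 10% random | 0.096 | 0.094 | 0.006 |
| 20% outcome-related / 10% random | 0.194 | 0.193 | 0.007 |
| 30% outcome-related / 10% random | 0.287 | 0.283 | 0.010 |
| 30% / 10%, same mechanism in both arms | 0.164 | 0.163 | 0.010 |
| 20% / 20%, same mechanism in both arms | −0.002 | −0.002 | 0.009 |

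In the first four rows the check would report stability while both estimates are wrong. In the last row both are right. The gap is about the same throughout, so it does not tell the two situations apart.

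**Rule of thumb.** When only experimental-arm dropout depends on outcome, bias ≈ share missing in that arm × gap between responders and non-responders not explained by observed data. This runs from 0.10 × 0.25 = 0.025 SD to 0.40 × 0.8 = 0.32 SD.

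**Does a missing-not-at-random analysis help?** A companion run with 20 imputations gave MICE estimates of 0.096, 0.195 and 0.278 SD in the first three scenarios. Lowering imputed experimental-arm values by an assumed 0.8 SD should remove 0.8 × share missing:
- 10%: 0.096 − 0.080 = 0.016 (simulated 0.015)
- 20%: 0.195 − 0.160 = 0.035 (simulated 0.035)
- 30%: 0.278 − 0.240 = 0.038 (simulated 0.041)

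The same shift would be wrong if dropout were in truth random: with 30%/10% random dropout it moved the estimate from −0.009 to −0.246 SD. A single shift is therefore no better founded than missing-at-random. What informs is a range, and the point at which the conclusion changes.

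**The case against.** **The SAP may cover this.** Only the protocol is at hand, and sensitivity analyses are often left to the SAP. That would answer a plain omission. Here, however, section 8.4 itself fixes the imputation method, the number of imputations and the stability check, so the limits of that check can be judged as written. The sentence does not claim to test missing-at-random; the risk is that stability will be read that way.

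**The mechanism is not in the documents.** A reader might infer that disengaged app users will be the ones who fail to answer, so that the benefit will be inflated. Section 5.3 speaks of the preventive population as a whole and names no arm, and the trial questionnaires reach all groups by REDCap email, not through the app (section 5.2). The last row of the table shows the bias cancelling. This objection stands: direction and size are plausible only.

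**The check is not blind by construction.** The experimental arm also records motivation, missions and repeated habit assessments in the app, and the MICE predictors are not listed. In a different scenario (20%/10% missing, an effect of 0.30 SD in responders and none in experimental-arm non-responders), an assumed week-8 app measure available for every experimental participant was added to the imputation. The full-sample effect was 0.24, the estimate without imputation 0.30 and MICE 0.26, a gap of about 0.04 SD. MICE then removes (0.30 − 0.26) / (0.30 − 0.24), about two-thirds, of the bias. This requires non-responders to keep using the app to week 8. It stands as a limit: the gap of 0.01 SD holds when only baseline informs the imputation.

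**The protocol's 5% and 10% do not size the bias.** The 5% difference in section 8.2 is an RCT input with no base rate. The limit in section 8.1, "with excessive missing data (>10% missingness in primary outcomes", is a feasibility hypothesis, not a dropout forecast. Counting every missing value as failure would give larger figures, but that is a convention and not the truth. This also stands.

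**It is a feasibility pilot.** Effectiveness is secondary, and at 90 per arm the standard error of about 0.13 SD is comparable with many of these biases. That lowers the priority but does not make the check informative about the assumption.

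**Conclusion.** The point holds in limited form. The with/without-MICE comparison can show whether results depend on imputing. It cannot show whether they survive outcome-related dropout, because both analyses rest essentially on the same assumption. If such dropout differs by arm, both can be biased in the same direction and the check will tend to report stability. If dropout and its mechanism are equal in the two arms, the bias largely cancels.

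The illustrative size is 0.09 to 0.29 SD of spurious effect at 10% to 30% outcome-related dropout in the experimental arm. It rests on the assumed rates, the assumed strength of the mechanism, random 10% dropout in control, and an imputation informed by arm and baseline only.

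A reader might also infer that the plan answers the wrong question, namely the effect had non-responders done as well as similar responders. The documents do not support this: missing-at-random is an assumption used to estimate the effect in those randomised, not a different target. Nor do they show that the pilot's estimate will be inflated. This is a worthwhile, inexpensive improvement and not a flaw that invalidates the pilot.

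**What to change.** In section 8.4:

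1. Keep the comparison with and without imputation, but describe it as a check on the imputation model, not on missing-at-random.
2. Add a missing-not-at-random sensitivity analysis on the same MICE run for the main 12-week outcomes. Use either a delta adjustment by arm over a stated range, reporting the shift at which the conclusion changes (tipping point), or control-based imputation for the experimental arm.
3. For seven-day abstinence, count missing as not abstinent as a further sensitivity analysis, labelled as a convention.

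In section 8.8, report the resulting range next to the main estimate wherever pilot effects inform the RCT sample size.

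The cost is a few sentences and a little extra code on imputations already planned, with no new data. Each added analysis carries its own untestable assumption, which is why a range is wanted, and the effect may look less favourable.

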8.5. Analysis of Primary and Secondary Endpoints

The pilot data will be analysed to determine the potential effectiveness of the iBeChange platform and to enhance the recommendation system. The analysis will account for confounding factors and

within-subject correlation over time, providing valuable information for the larger RCT and improving the accuracy of the feedback provided by the recommendation system.

Both the pilot and future RCT will involve a Bayesian Adaptively Randomised Design (BARD).

Compared to traditional frequentist trials, BARDs tend to be more efficient. They require smaller sample sizes as they allow multiple interim analyses without statistical penalties, enabling protocol refinements according to predefined rules. These designs can adapt allocation rules, sampling procedures, and the number of treatments tested, and they include a data-driven stopping rule to halt a treatment if it is effective, futile, or harmful.^{36,37}

A Bayesian hierarchical modelling approach will be used to estimate intervention effects while accounting for site-level variability. We will use Bayesian multilevel models to evaluate the preliminary effectiveness of the IBeChange intervention on tobacco and alcohol consumption, nutrition, physical activity, and psychosocial outcomes while accounting for the grouping related to the longitudinal follow-up and the hierarchical structure of the data (i.e., multiple observations from the same participant over time as well as participants grouped in different institutions). When compared to single-level regression models, its Bayesian counterpart can assess the expected correlation between measurements of the same individual and individuals in the same group, accounting for the dependency of these observations. This is accomplished by dividing the total variance into variations associated with the groups (level-2) and individual participants (level-1). As a result, such models estimate the variance component for the second level (i.e., the variability of the participant-specific estimates) or higher levels, indicating that the findings are accurate and generalisable.^{38,39}

Bayesian methods allow for the incorporation of existing knowledge about the probability of different model parameters (in the form of prior distributions) with observed data to generate updated knowledge about the parameters (in the form of posterior distributions). Statistical inferences are then made based on these updated distributions. We will use weakly informative priors, defined a priori based on clinical assumptions and literature, to derive posterior distributions. Sensitivity analyses will assess the robustness of results to different prior assumptions. Bayesian multilevel modelling is particularly well-fit to handle multiple comparisons. Under this framework, adjustment for multiple tests becomes unnecessary, allowing us to explore hypotheses at a granular level while decreasing the risk of reaching spurious conclusions. Furthermore, Bayesian analyses allow for direct probability statements about parameters (population-level results), providing precise parameter estimates without the need for large samples and allowing the determination of zero effects. Finally, Bayesian models provide more intuitively interpretable uncertainty estimates around parameter values than those offered by their frequentist counterparts.

We will implement the Bayesian estimates using the R statistical language⁴² with the rstanarm package,⁴³ which calls the stan package.⁴⁴ Our modelling strategy will use Markov Chain Monte Carlo (MCMC), repeated four times, i.e., four chains, with 1,000 warm-up iterations followed by 3,000 posterior sampling iterations per chain.

We will interpret model results as a point estimate representing the magnitude of each treatment effect (i.e., regression coefficient) and an interval estimate for the precision of that estimate. The median of the posterior distribution for each treatment effect constitutes the point estimate. We will

represent the posterior distribution of each treatment effect using 95% credible intervals (CrI). The 95% CrI is the smallest interval that contains the parameter values with the highest probability density (i.e., 95% credibility). Each interval estimate contains the range of the most reliable estimates for the magnitude of the treatment effect in light of the data, our model, the degree of random effect variability, and the sampling error. The posterior distribution's spread indicated the uncertainty of the estimate. Bayesian posterior probabilities will be employed to assess clinical effectiveness and futility for each primary outcome.

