8.6. Planned Interim Analyses

Interim analyses will occur after 25%, 50%, and 75% of the planned sample size have completed their 12-week follow-up assessments, at the end of the intervention. Interim analyses will evaluate effectiveness and futility parameters, allowing for data-driven trial modifications while ensuring scientific standards. Efficacy will be evaluated through predefined posterior probability thresholds, where the trial may stop early if the probability that the treatment effect exceeds the clinically meaningful threshold reaches 95%. Futility will be assessed to prevent unnecessary exposure to an ineffective intervention, with stopping criteria set for scenarios where the probability of a clinically insignificant effect exceeds 90%.

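### Section 8.5 says repeated looks cost nothing, but with a near-flat prior the fixed 95% rule in 8.6 doubles its false-declaration rate at the threshold, from 5.0% at one look to 10.1% over the three planned interims

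*Protocol*

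**What the plan says.** Section 8.5 presents the design for both studies: "Both the pilot and future RCT will involve a Bayesian Adaptively Randomised Design (BARD"). Among its advantages it lists: "They require smaller sample sizes as they allow multiple interim analyses without statistical penalties, enabling protocol refinements according to predefined rules".

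Section 8.6 fixes the looks: "Interim analyses will occur after 25%, 50%, and 75% of the planned sample size have completed their 12-week follow-up assessments". For efficacy, "the trial may stop early if the probability that the treatment effect exceeds the clinically meaningful threshold reaches 95"%. For futility, there are "stopping criteria set for scenarios where the probability of a clinically insignificant effect exceeds 90"%. The efficacy cut-off is the same at all three looks. No value is given for the threshold, and no cut-off is given for the final analysis.

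On priors, section 8.5 says: "We will use weakly informative priors, defined a priori based on clinical assumptions and literature", with sensitivity analyses over other priors. No prior scale is stated.

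Section 8.2 gives the size ("the estimated sample size for the pilot was 180 participants (90 per group")) and bases the RCT sample size on "a significance level of 0.05". Section 8.8 uses the pilot's effect estimate and variability to refine that sample size.

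**The concern.** Two properties are being run together. A posterior probability computed from the data in hand is still a valid posterior probability however many times one has looked. The chance that a fixed cut-off is crossed at some look when it should not be crossed rises with the number of looks. Section 8.5 denies any penalty without saying which property it means, and section 8.6 then uses a cut-off that is neither stricter early on nor described as calibrated.

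Two things are at stake. The first is how an early declaration of effectiveness may be read: a 95% cut-off invites the reading that the rule is wrong 5% of the time. The second is the estimate that comes with such a declaration. A stop at the first look rests on about 22 people per group, and only a large observed difference can trigger it. Section 8.8 then passes the pilot effect size into RCT planning, where an inflated value would make the RCT too small.

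**Working it through.** The protocol gives no false-positive rate for its stopping rule, so there is no stated figure to reproduce. The rate follows from the written rule.

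**Inputs from the protocol.** 180 participants, 90 per group (8.2); looks at 25%, 50% and 75% of the sample (8.6), about 22, 45 and 67 per group; efficacy cut-off 0.95 and futility cut-off 0.90 (8.6); weakly informative priors (8.5).

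**Assumptions.** Equal allocation throughout; one continuous outcome in SD units; flat prior for the main figure, with zero-centred normal priors of SD 2.5, 1 and 0.5 outcome SDs as the range; threshold δ from 0 to 0.3 SD; where a fourth look is shown, the 95% rule also applied at the final analysis.

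**Step 1, the rule as a test.** The standard error at full information is √(2/90) = 0.149 SD, and at information fraction t it is s = 0.149/√t. With a flat prior, P(effect > δ) ≥ 0.95 is the same as Z = (estimate − δ)/s ≥ 1.645. With a N(0, τ²) prior, the posterior variance is v = 1/(1/s² + 1/τ²), the posterior mean is m = v × estimate/s², and the rule is (m − δ)/√v ≥ 1.645.

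**Step 2, true effect exactly at the threshold, flat prior.** The correlation between looks i and j is √(tᵢ/tⱼ) for tᵢ < tⱼ. The chance of at least one crossing, by multivariate normal integration and by simulation, is:

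- one look: 5.0%
- three written interims: 10.1%
- four analyses (final at 95% assumed): 11.7%

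Using t statistics at 22, 45, 67 and 90 per group gives 11.8% for four analyses. Making the 90% futility rule binding leaves 11.7%.

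**Step 3, priors.** True effect at the threshold, δ from 0 to 0.3 SD:

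| Prior SD (outcome SDs) | Single final look | Three interims | Four analyses |
|---|---|---|---|
| 2.5 | about 5% | about 10% | 11.4-11.6% |
| 1 | 4-5% | 8-9% | 9.7-10.9% |
| 0.5 | 3-4% | 4-7% | 5.5-8.9% |

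**Step 4, true effect exactly zero, flat prior, four analyses.** The rate is 11.7%, 4.4%, 1.5% and 0.5% for δ = 0, 0.1, 0.2 and 0.3 SD. Repeated looks still multiply it: at δ = 0.2 SD a single final look gives about 0.14% and four looks give 1.5%.

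**Step 5, estimates at a wrong declaration.** Take the true effect and δ both at 0.2 SD with a flat prior. The estimate needed to cross is 0.2 + 1.645 × 0.149/√t: 0.69, 0.55, 0.48 and 0.45 SD at t = 0.25, 0.5, 0.75 and 1. The mean estimate at a wrong declaration is about 0.70 SD over the three interims and 0.67 SD over four analyses. For a single final look it is 0.2 + 0.149 × φ(1.645)/0.05 = 0.2 + 0.149 × 2.06 = 0.51 SD.

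**Step 6, a calibrated cut-off and its price.** With a flat prior, a constant cut-off of about 0.977 over the three interims, or 0.981 over four analyses, brings the rate at the threshold back to 5%. At 0.981, when the true effect is 0.3 SD above the threshold, early declarations fall from 61% to 44% and all declarations from 72% to 55%. At 0.2 SD above it, early declarations fall from 40% to 24%.

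**The case against.** The strongest reply is that this is a feasibility pilot. Section 8.1 places the statistical focus on feasibility rather than efficacy testing, effectiveness is secondary and preliminary, section 8.6 says the trial may stop rather than must, and the pilot claims no error rate. A Bayesian can fairly decline frequentist calibration here, and simulated operating characteristics are often left to a statistical analysis plan, which is not at hand. This stands as an argument against forcing a stricter cut-off on the pilot. It does not rescue the statement in 8.5, which the protocol makes itself and extends to the RCT.

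Three stronger readings are tempting and not supported.

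- A reader might take about 12% as the error rate of the written rule. That needs a fourth look at 95%, which section 8.6 does not state, and a near-flat prior. The three written looks give 10.1% with a flat prior and about 4-7% with a prior SD of 0.5.
- A reader might infer that the rule breaks the 0.05 in section 8.2. That figure is a significance level used to size the RCT, ordinarily an error rate under no effect, whereas the 10.1% is error at the threshold. Under no effect, the excess over 5% arises only at thresholds near zero (Step 4). The RCT's own looks and cut-offs are not in this document.
- A reader might blame the whole of the inflated estimate on repeated looks. Most of it comes from selecting on crossing: with a single look the excess over the true 0.2 SD is already 0.51 − 0.20 = 0.31, against 0.67 − 0.20 = 0.47 with four analyses, or about two-thirds.

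**Conclusion.** The concern holds in limited form. The no-penalty statement in 8.5 is true of the interpretation of posterior probabilities and false of the error rate of the rule in 8.6. With a near-flat prior and a true effect at the threshold, the three written interims double the false-declaration rate, from 5.0% to 10.1%. The 11.7% figure also assumes a final look at 95%. Priors with SD 1 or wider leave the three-look rate at about 8-10%; a prior SD of 0.5 brings it to about 4-7%, against 3-4% at a single final look. Because the protocol fixes neither the prior scale nor the threshold, the actual rate cannot be stated more closely than this.

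The practical consequence is confined to what an early declaration of effectiveness can be taken to show, and to the use of an early-stop estimate in planning the RCT. The pilot's feasibility aims are not affected.

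**What to change.** In section 8.5, delete the words claiming that interim analyses carry no statistical penalty. If the authors wish, they can say instead that posterior probabilities remain interpretable under repeated looks.

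In section 8.6, state that:

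- the false-declaration rate of the stopping rule, both at the threshold and at zero effect, is simulated under the final priors and reported with any early efficacy declaration;
- an effect estimate from an early stop is flagged as likely inflated when it is used for RCT sizing under section 8.8.

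Do not describe the 95% rule as having a 5% error rate. If the RCT is to claim 0.05, calibrate its cut-off to that level.

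These changes cost a few sentences and a short simulation. Raising the pilot's own cut-off to the values in Step 6 is optional: it loses a material share of true early declarations, and the values change with the prior and with whether a fourth look is counted.
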